However, currently it is not possible to predict which ARMS individuals will develop a psychotic disorder and which will not. This means that some ARMS individuals are having unnecessary treatment, and may be told that they are at high risk of psychosis when they are not, creating possible fear and stigma. It also means that the NHS may be using a costly treatment, (such as Cognitive Behaviour Therapy; CBT), in people who may not need it. For this reason, NIHR has commissioned research to improve the ability to predict people most at risk of psychosis, over and above the existing ARMS criteria, through the development of a refined prognostic tool. Such a tool will enable prediction of outcome for individual service users, enhance informed decision making, and to stratify the ARMS group into different risk profiles for the purposes of resource allocation and clinical trials. The prognostic tool has the potential to directly benefit service users through more focused services and treatments and could lead to the development of more cost-effective management plans in the NHS.

This project will involve a three-phase design:

Phase 1 will consist of an individual participant data evidence synthesis to identify factors associated with transition to psychosis. At the end of the evidence synthesis, decisions will be made about the best factors that will be included in the refined prognostic tool. Successful implementation of a prognostic model requires support by leading professionals in the field [13]. Measures also need to

be acceptable to service users. Thus, at the end of the evidence synthesis we will run focus groups to gauge opinion about the use of the individual measures in the prognostic tool. This will help ensure that the chosen measures are acceptable and feasible for routine use in the NHS. A major strength of the development of our tool is that it will only include prognostic factors which are measurable in an easy, quick and reliable way during routine care (i.e. without the need for expensive brain scanning or laboratory tests), thus optimising it as an efficient and cost-effective "bedside" tool for use in the NHS.

Based on the above findings, in **Phase 2** we will develop and internally validate a prognostic tool to better predict the later development of psychosis.

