Finally, **Phase 3** will be a cohort study of ARMS individuals with 12 month follow up to assess the external validity of the new prognostic tool. In addition, a valid prognostic tool could lead to more cost-effective pathways and management plans. To this end the project also includes health economic modelling.

2. Why this Research is Needed Now

Since April 2016 NHS England has required all Early Intervention in Psychosis Services to assess and manage individuals with an ARMS. This has resulted in a huge expansion in number of assessments and individuals accessing care at these services. While NHS England allocated additional funding for services, the extra demand has far exceeded that which was expected, resulting in larger caseloads and a strain on resources. Research to better stratify ARMS patients according to levels of risk of psychosis could reduce this strain, through more efficient use of NHS resources. Thus, those at highest risk could be offered CBT, while lower risk patients could be offered less costly and less intensive regular mental state monitoring. In this way, a prognostic tool that can be used in routine practice in Early Intervention Services will lead to the development of more cost-effective pathways and management plans.

While much ARMS research has attempted to identify the predictors of development of psychosis, including the development of prognostic models, no prognostic tool has yet been implemented in the NHS. Two recent systematic reviews summarised these ARMS studies [14, 15]. Both reviews found that only 7 studies of prognostic models in the ARMS group had any validation procedure. All 7 of these used internal validation only; that is, used the same sample that the model was derived from to test its predictive ability. None had any external validation. Furthermore, all 7 studies used pre-defined prognostic factors and so may have missed assessing other factors likely to be predictive of psychosis. Other problems included small sample sizes, poor reporting of missing data and low number of individuals developing psychosis relative to the number of predictor variables (i.e. low event to predictor variable (EPV) ratio, which might increase the risk of overfitting and overestimating the performance of the model [16, 17]). The development and external validation of one prognostic model has been published [18, 19] (not included in the above reviews).

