2b. Informed by the prognostic models and prognostic factors identified above, and feedback from service users and staff, state-of-the-art methodology will be used, including assessing apparent (calibration and discrimination of the model) and internal validation i.e. bootstrapped resampled estimates of calibration (how closely the probability of the event predicted by the model agrees with the observed probability [24]) and discrimination (the discriminative ability of the model as assessed by the c index [25]).

3. External validation of the model: predictive performance and acceptability

3a. Acceptability: At baseline assessment with the prognostic tool, acceptability will be examined by assessing whether any measures included in the tool were not completed and we will record reasons for this.

3b. The predictive performance of the tool: After 12 month follow up of the ARMS cohort we will evaluate the discrimination and the calibration of the tool and report our results in line with the best practice Transparent Reporting of a Multivariable Prediction Model for Individual Prognosis or Diagnosis (TRIPOD) guidelines [17].

3c. Through seeking consent at baseline to access health records for 2,3 and 5 year follow up, the long term predictive validity of the prognostic tool can be assessed in the whole sample in future studies.

4. To achieve Aim 4 we will conduct an exploratory cost-effectiveness analysis. We will explore the potential cost-effectiveness of the new prognostic tool compared to usual care (no prognostic tool) from the perspectives of the NHS and Social Care (costs) and service users (health benefits) over 1, 2 and 5 year time-horizons. We will use a cost-effectiveness acceptability approach to estimate the probability the new prognostic tool is cost-effective. A decision analytic model will capture transition between at risk, treated health states and the longer-term recovery/relapse cycle of psychosis. Probabilistic sensitivity analysis will account for data uncertainty. Structural uncertainty will be assessed in sensitivity, threshold and scenario analyses.

4. Research Plan

This project will (i) synthesise evidence, (ii) develop a prognostic tool for prediction of psychosis in ARMS individuals and (iii) test the tool's external validity and acceptability, and (iv) model the health economic impact of implementing this tool in clinical practice

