Exploratory cost-effectiveness analysis: We will explore the potential cost-effectiveness of the new prognostic tool compared to usual care (no prognostic tool) from the perspectives of the NHS and Social Care (costs) and service users (health benefits) over 1, 2 and 5 year time-horizons. The primary and sensitivity analyses will use a cost-effectiveness acceptability approach to estimate incremental cost-effectiveness ratios, probability the new prognostic tool is cost-effective and net benefit statistic and generate cost-effectiveness-acceptability curves (CEAC). The range of hypothetical willingness to pay thresholds (WTPT) to gain a unit of health benefit values for the analyses will be £0 to £30,000, with a mid-estimate of £15,000 for the main analyses [86, 87]. For the primary analysis, the measure of health benefit for the primary analysis will be the quality adjusted Life year (QALY) and direct costs of health and social care services will be estimated (primary, secondary and community physical and mental health care; social care). Sensitivity analyses will explore the impact of using (i) alternative measures of health benefit (ii) including indirect costs of lost productive activity in the cost estimates. Threshold and scenario analyses will be used to explore the minimum level of effectiveness the prognostic tool needs to achieve to be cost-effective.

A decision analytic model will be used for all the analyses. The decision model structure, assumptions and data estimates will be developed iteratively from the reviews and analyses in Phases 1, 2 and 3 and structured discussions with key stakeholders (service users and health care professionals) and the research team at Investigator and Project Steering Committee meetings and through established service user networks in Manchester, the North East and Birmingham (face validity) [88]. Two researchers (Health Economics Research Fellow and [name]) will independently build and populate the model (internal validity). Sections of the model will be used to predict events/health states, costs and QALYs observed in the prospective cohort study and published literature (external validity).

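### With usual care as the only named comparator, the cost-effectiveness analysis cannot separate the value of prediction from the effect of treating fewer people

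*Protocol*

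**What the plan says.** Objective 4 in Protocol section 3 sets out to study the "potential cost-effectiveness of the new prognostic tool compared to usual care (no prognostic tool"), and adds: "We will use a cost-effectiveness acceptability approach to estimate the probability the new prognostic tool is cost-effective". Section 4.3.12 repeats the contrast, "We will explore the potential cost-effectiveness of the new prognostic tool compared to usual care (no prognostic tool"), and lists its outputs: incremental cost-effectiveness ratios, the "probability the new prognostic tool is cost-effective and net benefit statistic", and acceptability curves. Willingness to pay runs from £0 to £30,000, "with a mid-estimate of £15,000 for the main analyses".

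The mechanism is described earlier. Section 1 says that "the NHS may be using a costly treatment, (such as Cognitive Behaviour Therapy; CBT), in people who may not need it". Section 2 says that "those at highest risk could be offered CBT, while lower risk patients could be offered less costly and less intensive regular mental state monitoring".

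The nearest safeguard is the set of threshold and scenario analyses in section 4.3.12, meant to "explore the minimum level of effectiveness the prognostic tool needs to achieve to be cost-effective". Effectiveness is not defined there, and no strategy other than the tool and usual care is named. The probabilistic and structural sensitivity analyses in the same section name none either.

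**The concern.** A tool that leads to fewer people receiving CBT changes costs and outcomes in two ways. It lowers the number treated, which any rule treating the same share would also do. It may also pick out the people who gain most, which only prediction can do. A single comparison with usual care reports the sum of the two.

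If CBT is poor value for the average patient at the chosen threshold, the first effect alone can make the tool look cost-effective. If CBT is good value, a tool that predicts usefully can look poor because it withholds treatment. In both cases the headline figure says more about CBT than about prediction. This matters because section 6 lists an economic model intended to guide implementation across NHS services.

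**Working it through.** **The plan's own figures.** The protocol gives no cost-effectiveness result to reproduce. Two of its figures are used here. The main threshold of £15,000 is the midpoint of £0 and £30,000. The 12-month transition rate is 20% (section 4.3.6; 558 × 0.20 = 111.6, the stated 112).

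**Algebra, with no assumed costs.** Let u be the share given CBT under usual care, q the smaller share under the tool, B the net benefit of CBT over monitoring per average patient, and k the tool's cost per person. Section 4.3.12 puts a c index of 0.5 at no better than chance, so such a tool treats a random share q.

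- Usual care against monitoring for all: uB, taking those treated as average patients.
- Tool with c = 0.5 against monitoring for all: qB - k.
- Difference: (qB - k) - uB = -(u - q)B - k.

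This is positive when B < -k/(u - q). With assumed values of k from £20 to £100, the condition is:

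| u | q | k = £20 | k = £100 |
|---|---|---|---|
| 1.0 | 0.5 | B < -£40 | B < -£200 |
| 0.7 | 0.5 | B < -£100 | B < -£500 |

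**Illustration.** From the protocol: threshold £15,000 and transition rate 20%. Assumed: CBT costs £1,000, relative risk of transition 0.5, loss per transition 0.2 QALY and £5,000, u = 1, q = 0.5, k = £20.

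- Value of one averted transition: 0.2 × £15,000 + £5,000 = £8,000.
- Expected gain per person treated: 0.20 × (1 - 0.5) × £8,000 = £800.
- B = £800 - £1,000 = -£200.
- c = 0.5 tool against usual care: -(0.5)(-£200) - £20 = **+£80**.
- Monitoring for all against usual care: +£200. The c = 0.5 tool against monitoring for all: £80 - £200 = **-£120**.
- A c = 0.7 tool (binormal score) gives +£261 against usual care and £261 - £200 = **+£61** against monitoring for all.

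Against usual care both tools look favourable. Only the added strategy separates them. The gap of £261 - £80 = £181 is the part due to prediction.

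**No treatment effect.** With relative risk 1.0 and CBT at £1,000, B = -£1,000. The tool's net benefit against usual care is 0.5 × £1,000 - £20 = £480 at c = 0.5, 0.6, 0.7 and 0.8 alike.

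**The opposite sign.** With CBT at £500 and the other inputs unchanged, B = £800 - £500 = +£300. The c = 0.5 tool then has -(0.5)(£300) - £20 = -£170, so usual care as sole comparator does reject it.

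**The case against.** Four arguments on the other side carry weight.

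- **There is no decision rule.** The analysis is labelled exploratory and sets no pass mark. A reader might infer that a useless tool would be declared cost-effective whenever CBT is poor value. The text does not support that: nothing is declared, the tool's cost must be covered first, and the share receiving CBT under usual care is not stated. If usual care already directs CBT to those who gain most, the random tool does worse than the formula shows.
- **The model is still to be built.** Section 4.3.12 says it will be developed iteratively, and nothing excludes further strategies. But the comparator is a stated choice, made in two places, and no other section adds to it.
- **Other results would give warning.** Discrimination and calibration are assessed separately, and a threshold analysis taken down to c = 0.5 could find that no minimum accuracy is needed. That would be a useful hint. The headline ratio and probability would still not carry it.
- **Usual care is the right comparator for implementation.** This stands. Section 1 notes that services are required to treat this group, so monitoring for all may not be an available policy. It belongs in the model as a reference scenario only.

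A reader might also attach a probability to the problem. One simulation with assumed inputs (mean CBT cost £1,500) gave a c = 0.5 tool a 0.70 to 1.00 chance of looking cost-effective at £15,000. Those inputs largely fix the answer. Break-even at relative risk 0.5 is £1,500 / (0.20 × 0.5) = £15,000 per averted transition, and the most favourable inputs reach only 0.3 × £15,000 + £8,000 = £12,500. With 0.6 QALY and £15,000 per transition, equally assumed, the value is £24,000, CBT gains 0.1 × £24,000 - £1,500 = £900, and the useless tool is rejected.

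**Conclusion.** The point holds as a limit on what the planned comparison can show. It is not a forecast of a wrong conclusion. When CBT's average net benefit lies below -k/(u - q), a tool with no predictive ability has positive incremental net benefit against usual care, and a favourable acceptability curve would not show that prediction adds value.

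The algebra assumes that the tool reduces the share treated and that those treated under usual care are average patients. The pound figures are illustrations: only the £15,000 threshold and the 20% transition rate come from the protocol. How often the condition would be met cannot be known from the protocol. This is a cheap improvement to an exploratory analysis.

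**What to change.** In section 4.3.12:

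1. Keep usual care as the comparator for the implementation question.
2. Add two reference strategies to the decision model: a null tool (the same share treated as under the tool, chosen without regard to risk), and monitoring for all as a scenario. Both are for modelling only and imply no change to anyone's care.
3. Report incremental net benefit and acceptability curves across all the strategies.
4. Define effectiveness in the threshold analysis as the c index, or sensitivity and specificity, and run it against the best strategy that does not use the tool.
5. State the share treated under usual care and the tool's cost per person as model inputs.

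The cost is a little more modelling in a Markov model already anticipated, largely with inputs it needs anyway and with no new data collection in the cohort. The reported probability of cost-effectiveness may come out less favourable.

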Appendix 1 - EXAMPLE SEARCH FOR THE ECONOMIC EVAULUATIONS REVIEW (EMBASE)

- 1 psychosis/ or psychosis.mp.
- 2 (clinically at high risk or clinically at risk or clinical high risk or ultra-high risk or prodrom* or at risk mental state or risk of psychosis or ARMS or prodromal psychosis).mp.
- 3 1 and 2
- 4. Health Economics/
- 5. exp Economic Evaluation/
- 6. exp Health Care Cost/
- 7. exp Pharmacoeconomics/
- 8. 6 or 7 or 8 or 9
- 9. (econom\$ or cost or costs or costly or costing or price or prices or pricing or pharmacoeconomic\$).ti,ab.
- 10. (expenditure\$ not energy).ti,ab.
- 11. (value adj2 money).ti,ab.
- 12. budget\$.ti,ab.
- 13. 11 or 12 or 13 or 14
- 14. 10 or 15
- 15. letter.pt.
- 16. editorial.pt.
- 17. note.pt.
- 18. 17 or 18 or 19
- 19. 16 not 20
- 20. (metabolic adj cost).ti,ab.
- 21. ((energy or oxygen) adj cost).ti,ab.
- 22. ((energy or oxygen) adj expenditure).ti,ab.
- 23. 22 or 23 or 24
- 24. 21 not 25
- 25. exp Animal/
- 26. exp Animal/
- 27. exp Animal Experiment/
- 28. Nonhuman/
- 29. (rat or rats or mouse or mice or hamster or hamsters or animal or animals or dog or dogs or cat or cats or bovine or sheep).ti,ab.
- 30. 27 or 28 or 29 or 30 or 31
- 31. exp Human/
- 32. exp Human Experiment/
- 33. 33 or 34
- 34. 32 not (32 and 35)
- 35. 26 not 36
- **36.** 3 and 37

Appendix 2 DATA ITEMS TO BE EXTRACTED FOR THE ECONOMIC REVIEW

Study details
Title of paper
Author(s)
Journal title, Year, Vol. (issue): pages
Subject of study
Intervention(s)
Comparator(s)
Country and setting
Time horizons
Condition
Study question and perspective(s)
Key elements
Type of economic analysis
Study population
Modelling study? (y/n); If yes, basic model details
Were costing and effectiveness inputs derived from the same patient sample?
Clinical evidence
List the clinical inputs included
Data sources
Methods to obtain data
Measures of health benefit
Summary measure of health benefit
If no measure of health benefit: was an adequate cost-minimisation argument made? (y/n/NA)
Utility values: whose values?
Utility values: how were they elicited?
Discounting of health outcomes
Direct costs
List the types of direct cost included
Describe who bears these costs
Source of resource use data (primary, secondary, assumptions?)
Are resource use and cost inputs reported separately?
Sources of unit prices
Currency and price year
Price adjustments
Do the authors report excluding any direct cost items?
Discounting of direct costs
Indirect costs
Are any indirect costs included? (If no, NA for rest of section.)
List the types of indirect cost included
Describe who bears these costs
Source of resource use data (primary, secondary, assumptions?)
Are resource use and cost inputs reported separately? (y/n)
Sources of unit prices
Currency and price year
Price adjustments
rnice aujustinents

Do the authors report excluding any indirect cost items? Discounting of indirect costs Statistical summary of costs Descriptive statistics reported Was a test used to determine whether there is a statistically significant difference in costs? Was the study powered to detect cost differences? **Analysis of uncertainty** If model: was parameter uncertainty explored? If model: were all parameters included? If model: was structural uncertainty explored? If not model: was variation in patient-level data explored? All studies: were alternative subgroups / settings explored? All studies: was value of information analysis performed? Results: Estimated benefits (if applicable) Average and incremental measures of benefit (bullet point per comparison) Did the duration of benefit match the observed data? Were adverse effects captured in the measure? **Results: Estimated costs** Total cost: intervention arm(s) Total cost: comparator arm(s) Incremental cost (column per comparison) Were adverse effect costs included? Result of statistical test for difference in costs Did the duration of costs match the time horizon? Synthesis of benefits & costs, and conclusions How were benefits and costs combined? Summary results (eg ICER; CEAC) Important differences in results for subgroups or sensitivity analyses. Summary of authors' conclusions **Critical review** Is the choice of comparator suitably justified? If model: was the model structure suitable? If model: was a model schematic presented? If model: was the model adequately reported? Validity of primary effectiveness data Validity of secondary effectiveness data Validity of estimated health benefit Validity of estimated costs Do the authors discuss the generalisability of their findings? Do the authors compare their findings to previous studies? Strengths mentioned by the authors Limitations mentioned by the authors Are the authors' conclusions justified? **Implications**

Do the authors describe policy implications of their findings? Are they appropriate?

Do the authors describe research recommendations? Are they appropriate?
